#### 6.2.8. Study Drug Administration/Dispensing/Return

Detailed instructions on administration of duvelisib can be found in [Section 7](#).

### 6.3. Treatment Termination Assessments for Subjects Receiving Duvelisib

Assessments to be performed at the TT Visit are presented in [Table 1](#). The TT Visit should be scheduled no more than 7 days after the decision to terminate duvelisib. Assessments performed within the previous 2 weeks, or previous 30 days for investigator response assessments, need not be repeated at the TT Visit.

Subjects who discontinue duvelisib and have not withdrawn consent from overall study participation will enter the survival follow-up period as determined by the previous study.

If the subject withdraws consent from overall study participation and not just treatment with duvelisib, no further attempts should be made to collect additional data from these subjects.

### 6.4. Safety Follow-up Assessments for Subjects Receiving Duvelisib

All subjects will have a Safety Follow-up Visit approximately 30 (+ 7) days after the last dose of duvelisib. At a minimum, this visit should include collection of AEs/SAEs and concomitant medications and procedures. The Safety Follow-up Visit can be performed by telephone call as long as the subject does not require laboratory and/or other procedures related to any new or ongoing AEs, in which case a clinic visit will be required.

### 6.5. Survival Follow-up Assessments for All Subjects

Subjects receiving duvelisib treatment will be followed for OS after discontinuation of duvelisib as indicated in [Table 1](#). Subjects enrolled only in the survival follow-up portion of this study will be assessed according to [Table 2](#).

All subjects will be followed for OS for the duration of time outlined in their previous duvelisib study. Survival follow-up will occur every 6 months ( $\pm$  4 weeks). Information on initiation of

other anticancer therapy will also be collected and should include therapy name(s), start and stop date(s) of other subsequent therapies, as well as the best response on the subsequent therapies, as applicable. This assessment can be conducted by telephone interview.

## **6.6. Concomitant Medications for Subjects Receiving Duvelisib**

The recommendations and restrictions in this section apply only to subjects receiving duvelisib.

### **6.6.1. Antimicrobial Prophylaxis**

Antimicrobial prophylaxis should be continued as prescribed in the subject's previous duvelisib study.

### **6.6.2. Transfusion and Growth Factor Support (Prophylaxis or Supportive Care)**

At any time during treatment, blood cell transfusion (packed RBCs or platelets) to maintain a subject's hemoglobin level  $\geq 8.0$  mg/dL or platelet count  $\geq 10,000/\mu\text{L}$  is recommended.

Transfusions may be used at any time as clinically indicated.

Hematopoietic growth factors may be used at the discretion of the Investigator and in accordance with standard cancer treatment guidelines. Prophylactic use of growth factors such as granulocyte-colony stimulating factor (G-CSF) or PEGylated G-CSF may be implemented if clinically indicated, in accordance with local guidelines and medical practice (eg, if a subject has Grade 4 neutropenia for  $\geq 7$  days, febrile neutropenia, or according to the National Comprehensive Cancer Network practice guidelines for myeloid factors). Subjects on a stable dosage of erythropoietin to treat baseline anemia may continue on this therapy at this dosage.

### **6.6.3. Prohibited: Use of Vaccines**

For all subjects, the use of live or live attenuated vaccines is prohibited during the treatment with duvelisib.

The use of inactivated (or killed) vaccines is allowed during the study; however, subjects and their physicians should be aware that the effectiveness of any vaccine administered concomitantly with duvelisib may be diminished. The ability to generate an immune response to any vaccine after the administration of duvelisib has not been studied.

### **6.6.4. Prohibited: Immunosuppressants**

Subjects are not to receive ongoing treatment with chronic immunosuppressants (eg, cyclosporine) or systemic steroids for  $> 1$  week at doses greater than the equivalent of 20 mg prednisone once daily (QD).

Note: Acute treatment for underlying autoimmune disorders (eg, reactive airway disease, rheumatoid arthritis) with corticosteroid doses  $> 20$  mg prednisone or equivalent QD for  $\leq 1$  week is permitted during the study. Corticosteroid doses of  $\leq 20$  mg prednisone or equivalent QD are permitted during the study for physiological replacement or chronic treatment for underlying autoimmune disorders (eg, reactive airway disease, rheumatoid arthritis).

6.6.5. Prohibited: Other Anticancer Therapy or Investigational Agents

Subjects receiving duvelisib are not to receive any additional anticancer therapy or other investigational agents not outlined in the protocol.

6.6.6. Prohibited: Medications or Food that Inhibit or Induce Cytochrome P450 3A4

In vitro data indicate cytochrome P450 (CYP) 3A4 plays an important role in the metabolism of duvelisib; therefore, the concomitant use of drugs or foods that are strong inhibitors or inducers of CYP3A are not allowed during study treatment with duvelisib.

[Appendix 1](#) provides a list of medications known to be strong inhibitors or inducers of CYP3A. However, it should be noted that this is not a comprehensive list of all medications that may modulate CYP3A activity.

Subjects should avoid eating grapefruits or grapefruit-containing products. In addition, subjects should avoid herbal supplements including, but not limited to, St. John's wort throughout the study as this is known to be a strong inducer of CYP3A.

The Sponsor should be contacted with any questions regarding concomitant use of medications that are thought to modulate CYP3A activity. The concomitant use of moderate or weak inhibitors may be allowed in selected circumstances after consultation with the Medical Monitor.

6.6.7. Use with Caution: Medications that are Substrates of CYP3A or CYP2C8

In vitro studies have demonstrated duvelisib is an inhibitor of CYP3A4. Coadministration of duvelisib with midazolam, a sensitive CYP3A substrate, resulted in an approximate 4-fold increase in the midazolam. Systemic exposure to other medications that are substrates for CYP3A may be increased in subjects receiving duvelisib. Caution should be used if duvelisib is administered concomitantly with drugs that are substrates for CYP3A, particularly those with a narrow therapeutic range. Drugs that are substrates for CYP3A should be used only if medically necessary and therapeutic alternatives are not available.

Duvelisib is an inhibitor of CYP2C8 in vitro. Physiologically based pharmacokinetic modeling indicates that the inhibitory effect of duvelisib on CYP2C8 substrates is not expected to be clinically meaningful at a duvelisib dosage of 25 mg BID. The predicted mean area under the concentration-time curve ratio for rosiglitazone (a CYP2C8 substrate) with and without duvelisib at 25 mg BID was 1.02. Inhibition of CYP2C8 metabolism appears to be negligible, and only minor changes in the systemic exposure to CYP2C8 substrates are anticipated in the presence of duvelisib. Medications that are metabolized via CYP2C8 may be used as medically indicated but with caution.

[Appendix 2](#) provides a list of medications known to be substrates of CYP3A or CYP2C8. It should be noted that this is not a comprehensive list of all medications that may be substrates of CYP3A or CYP2C8. The Sponsor should be contacted with any questions regarding concomitant use of medications that are CYP3A or CYP2C8 substrates.

#### 6.6.8. Use with Caution: Medications that are Substrates or Inhibitors of P-glycoprotein

In vitro data indicate duvelisib is a substrate for P-glycoprotein (P-gp) and may have the potential to inhibit the activity of P-gp. P-glycoprotein substrates or inhibitors may be used as medically indicated but with caution.

[Appendix 3](#) provides a list of medications that are substrates or inhibitors of P-gp. It should be noted that this is not a comprehensive list of all medications that may be substrates of P-gp or may modulate P-gp activity. The Sponsor should be contacted with any questions regarding concomitant use of medications that are thought to modulate P-gp activity.

#### 6.6.9. Other Concomitant Therapies

Any other medication that is considered necessary for the subject's welfare and that is not expected to interfere with the evaluation of duvelisib may be given at the discretion of the Investigator.

#### 6.6.10. Photosafety

The effect of duvelisib on the skin, especially when in direct sunlight or with artificial ultraviolet (UV) light (eg, tanning booths) is not known. As a general precaution, subjects should be advised to use appropriate protective measures to minimize exposure to direct sunlight or UV light sources while receiving duvelisib and for at least 30 days after the last dose.

#### 6.6.11. Contraception and Pregnancy

The effects of duvelisib on conception, pregnancy, and lactation are unknown.

At screening, all male and female subjects who are not surgically sterile or postmenopausal must agree to use medically acceptable methods of birth control for the duration of the study and for 30 days after the last dose of duvelisib. Acceptable forms of contraception for females are nonhormonal and hormonal intrauterine devices, hormonal birth control pills, hormonal birth control patches, hormonal birth control injections, or hormonal birth control implants. Sexually active men, and women using contraceptive methods described above, should also use barrier contraception with spermicide. Acceptable barrier forms of contraception are condoms or diaphragms.

The use of birth control methods is not required if the male partner (of the female subject) has a documented history of a vasectomy or if the female partner (of the male subject) has a documented history of bilateral oophorectomy, hysterectomy, tubal ligation, or if she is > 55 years of age and postmenopausal for at least 1 year.

Male subjects should not donate sperm for 3 months after the last dose of duvelisib.

## 7. INVESTIGATIONAL MEDICINAL PRODUCT

### 7.1. Duvelisib

#### 7.1.1. Description of Investigational Medicinal Product

Duvelisib drug substance is a white to off-white crystalline powder. The duvelisib drug product is formulated in 2 different capsule strengths (5 mg and 25 mg) for oral delivery with excipients (diluent, glidant, disintegrant, and lubricant) that are listed in the United States Food and Drug Administration Inactive Ingredients Database for approved drug products and/or Generally Regarded as Safe. Additional information is provided in the IPI-145-23 Pharmacy Manual.

#### 7.1.2. Dosage

Duvelisib is administered as an oral capsule supplied by the Sponsor.

For subjects continuing on duvelisib treatment:

- Oral duvelisib BID over 28-day cycles at the dose level received in the previous study.

Dose holds up to 42 days are permitted for management of treatment-related AEs.

Dose reductions and discontinuations for individual subjects may be made based on the clinical judgment of the Investigator with notification to the Sponsor's Medical Monitor (see [Section 7.2](#)).

#### 7.1.3. Administration

Duvelisib should be self-administered orally BID (every  $12 \pm 2$  hours) in 28-day cycles. The morning dose will be administered in the clinic on C1D1. An attempt should be made to enable each dose to be taken at approximately the same time of day. Missed doses outside the windows defined above or vomited doses should not be retaken or repeated.

Duvelisib capsules should be swallowed whole with a glass of water (approximately 8 ounces or 240 mL). Duvelisib may be administered without regard to meals; however, subjects must avoid grapefruit and grapefruit juice while on duvelisib.

### 7.2. Dose Holds and Modifications

Subjects will be monitored continuously for toxicity while on duvelisib. Toxicity will be assessed using the National Cancer Institute (NCI) Common Terminology Criteria for Adverse Events (CTCAE), Version 4.03 or higher. If a subject has an AE at least possibly related to duvelisib, then dose holds with possible modifications as described in [Table 4](#) may be implemented. Adjustments to these guidelines may occur based on the clinical judgment of the Investigator with notification to the Sponsor's Medical Monitor.

**Table 4: Dose Holds for Treatment-related Adverse Events**

| Treatment-related Toxicity a,b                              | Duvelisib c   |
|--|--|
| Hematologic   |  |
| ≥ Grade 3 FN   | Hold until afebrile and negative culture                                 |
| ≥ Grade 3 Thrombocytopenia with ≥ Grade 2 Hemorrhage                   | Hold until no evidence of hemorrhage and stabilization of platelet count |
| Other Grade 4 Hematologic Toxicity (excluding FN and Thrombocytopenia) | Continue   |
| Nonhematologic  |  |
| ≥ Grade 2 Pneumonitis/Pneumonia  | Hold until completion of course of therapy and resolution of symptoms    |
| ≥ Grade 3 Nonhematologic Toxicity                                      | Hold until ≤ Grade 1 or return to Baseline                               |

Abbreviations: AE = adverse event; CTCAE = Common Terminology Criteria for Adverse Events; FN = febrile neutropenia.

a Treatment-related AEs: possible, probable, or definite relationship to duvelisib.

b Toxicity grades are defined per CTCAE Version 4.03. Note if a parameter is not defined by CTCAE, then AE grading criteria ([Section 8.2.1.2](#)) should be utilized.

c Dosages of duvelisib may be reduced after subsequent occurrences of the same treatment-related AE. See [Section 7.2.1](#) for more information on dosing modification and discontinuation.

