### 7.2.1. Duvelisib Dosing Modifications and Discontinuation

As described in [Table 4](#) and in [Section 7.2.1.1](#) (treatment hold for hematologic toxicities) and [Section 7.2.1.2](#) (treatment hold for nonhematologic toxicities), duvelisib should be held upon the first occurrence of certain toxicities. Upon resolution of the AE, duvelisib treatment should be reinitiated at the current dose level according to the guidelines in [Table 4](#). On subsequent occurrences of the same event, duvelisib should be reinitiated at 1 dose level lower than current dose level (see [Table 5](#)). Duvelisib may be held up to 42 days because of treatment-related AEs. Doses held for > 42 days because of treatment-related AEs will result in permanent discontinuation from duvelisib. Any subject who requires a dose-level reduction to below 10 mg BID because of treatment-related AEs will be permanently discontinued from duvelisib treatment.

Subjects who discontinue duvelisib should return to the clinic for the TT Visit assessments and may continue to be followed for OS based on the length of survival follow-up defined in the subject's previous study.

Dose levels for duvelisib are shown in [Table 5](#).

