#### 7.2.1.2. Treatment Hold for Nonhematologic Toxicity

Treatment with duvelisib should be held for Grade 2 or higher pneumonitis/pneumonia or Grade 3 or higher other nonhematologic toxicities:

- Grade 2 or higher pneumonitis/pneumonia, defined as symptomatic and requiring medical intervention, including oral antimicrobials and/or steroids:
  - New onset or worsening of cough, shortness of breath, hypoxia, or new radiographic findings should be evaluated for pneumonitis. If pneumonitis is suspected, duvelisib should be held, and administration of corticosteroids considered while the infectious etiology is being determined. Restarting treatment with duvelisib is allowed after completion of the course of therapy and complete resolution of symptoms.

- Grade 3 or higher other nonhematologic toxicities including the following:
  - Infections: Subjects who develop infections requiring intravenous treatment with antibiotics/antifungals/antivirals should have duvelisib held until the infection resolves (subject may restart duvelisib when completing a course of oral therapy). Prophylaxis to prevent recurrent/opportunistic infections will not preclude the subject from restarting treatment.
  - Hepatic events: Subjects who develop Grade 3 or higher transaminase (ALT/AST) elevations with or without clinical symptoms should have duvelisib held until the values return to baseline. Duvelisib should be reintroduced after laboratory values have remained at baseline levels for at least 1 week. Additional work-up to evaluate viral infection/reactivation, exposure to environmental toxins (eg, alcohol/concomitant medications), or other causes is recommended before restarting treatment with duvelisib.

If ALT/AST elevations  $\geq$  Grade 3 recur upon rechallenge with duvelisib, hold duvelisib, and administer corticosteroids. A reduced dose of duvelisib may be reintroduced after laboratory values have remained at baseline levels for at least 1 week.

Any subject with new evidence of hepatitis B surface antigen seropositivity or other evidence of hepatitis B reactivation will be discontinued from duvelisib.

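### Protocol Table 4 and Section 7.2.1.2 set different restart conditions after Grade 3 or higher nonhematologic toxicity, and no sentence says which governs

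*Protocol*

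**What the plan says.** Table 4 of the protocol puts every treatment-related nonhematologic toxicity of Grade 3 or higher in one row, with the instruction "Hold until ≤ Grade 1 or return to Baseline". The only nonhematologic event with its own row is pneumonitis/pneumonia, and that row agrees with Section 7.2.1.2.

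Section 7.2.1.2 treats several members of the same category separately. After ALT/AST elevation, subjects "should have duvelisib held until the values return to baseline", and then: "Duvelisib should be reintroduced after laboratory values have remained at baseline levels for at least 1 week". After nausea, vomiting or diarrhea, after rash, and after new cardiac events (QTcF prolongation included), the hold lasts until symptoms have resolved. An infection that needs intravenous treatment must resolve, and restart is allowed when an oral course is being completed.

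On how the two fit together, Section 7.2.1 cites Table 4 alongside both subsections when it describes holds ("treatment hold for nonhematologic toxicities), duvelisib should be held upon the first occurrence of certain toxicities"). For restarting it cites Table 4 alone: after resolution, "duvelisib treatment should be reinitiated at the current dose level according to the guidelines in" Table 4. Section 7.2 adds: "Adjustments to these guidelines may occur based on the clinical judgment of the Investigator", with notice to the Medical Monitor.

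On the limit, Section 7.1.2 says: "Dose holds up to 42 days are permitted for management of treatment-related AEs". Section 7.2.1 says: "Doses held for > 42 days because of treatment-related AEs will result in permanent discontinuation from duvelisib".

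On the Treatment Termination (TT) visit, Section 4.3 allows 7 days from the last dose. Section 6.3 and Table 1 footnote b allow 7 days from the decision to stop.

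**The concern.** Two parts of the dosing instructions answer the same question differently: when may a subject go back on drug after a severe toxicity? After a first event the restart is at the current dose, so a site that follows the looser text re-exposes the subject at full dose with incomplete recovery.

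Safety is the primary objective. Grade 3 or higher transaminase elevation, diarrhea, rash and infection are categories of special interest in SAP Appendix A, and Protocol Section 10.7 provides no external monitoring committee.

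There is a smaller effect on the data. Both texts start the hold at the same grade, so the count of subjects with any hold does not depend on the restart rule. Hold length, and through it relative dose intensity (SAP 7.1.3), can depend on it. So can the count of discontinuations (SAP 7.1.3) and the table of treatment-emergent events leading to discontinuation (SAP 7.3.1).

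**Working it through.** **Restart conditions side by side** (treatment-related, Grade 3 or higher)

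| Event | Table 4 | Section 7.2.1.2 | Where they part |
|---|---|---|---|
| ALT/AST elevation | Grade 1 or less, or baseline | Baseline, kept for at least 1 week | Always, by 7 days or more |
| Nausea, vomiting, diarrhea | Same | Symptoms resolved | While Grade 1 symptoms remain |
| Rash | Same | Symptoms resolved | While Grade 1 rash remains |
| Infection needing intravenous treatment | Same | Infection resolved; restart allowed when completing an oral course | A different kind of criterion |
| Cardiac, including QTcF | Same | Symptoms resolved | Residual symptoms; no threshold in 7.2.1.2 if there are none |

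The protocol gives no figure to reproduce. The arithmetic is day counting.

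**Inputs.** Hold limit 42 days (7.1.2, 7.2.1); 1 week = 7 days at baseline (7.2.1.2); TT window 7 days (4.3, 6.3, Table 1 footnote b). Assumptions: day 0 is the last dose, and grade and baseline status are known daily.

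**ALT/AST gap.** Let g be the first day Table 4 is met and b the day baseline is reached and then kept. Baseline itself satisfies Table 4, so g ≤ b.
- Table 4 restart day = g
- Section 7.2.1.2 restart day = b + 7
- Gap = b + 7 − g, which is at least 7 days

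**Effect of the limit.** The protocol does not define how hold days are counted, so both counts are shown.
- Count A (hold = restart day − 0): latest restart is day 42, so Section 7.2.1.2 needs b ≤ 42 − 7 = 35. The texts give opposite outcomes when g ≤ 42 and b ≥ 36.
- Count B (hold = dose-free days = restart day − 1): latest restart is day 43, so b ≤ 43 − 7 = 36. The texts give opposite outcomes when g ≤ 43 and b ≥ 37.
- If g = b, the window of opposite outcomes is days 36–42 (A) or 37–43 (B), 7 days either way.

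| g | b | Table 4 restart | 7.2.1.2 restart | Count A | Count B |
|---|---|---|---|---|---|
| 20 | 34 | 20 | 41 | allowed | allowed |
| 30 | 37 | 30 | 44 | over limit | over limit |
| 36 | 36 | 36 | 43 | over limit | allowed |
| 36 | 40 | 36 | 47 | over limit | over limit |

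The last two columns say whether the Section 7.2.1.2 restart falls within the limit. A subject who stays at Grade 1 above baseline may restart under Table 4 but never qualifies under Section 7.2.1.2.

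In practice the days fall on visits, since the default is re-evaluation at least weekly. The cutoffs therefore show where the rules part, not which subjects will be affected.

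**TT visit.** The Section 4.3 deadline is day 7. If the hold limit itself triggers the decision, that is day 43 (A) or 44 (B). The Section 4.3 deadline then passed 43 − 7 = 36 or 44 − 7 = 37 days earlier. The Section 6.3 deadline is 43 + 7 = day 50 or 44 + 7 = day 51. The decision could come sooner, but any decision after day 7 already misses the Section 4.3 deadline.

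**The case against.** The strongest reply is that Table 4 is a summary and Section 7.2.1.2 is its elaboration. Table 4 footnote c sends the reader to Section 7.2.1. Section 7.2.1.2 lists these events as members of the Table 4 category, and its closing paragraph makes Table 4 the default where nothing else is specified. Section 7.2.1 makes resolution the precondition for restart, and its main contrast is dose level: current dose after a first event, one level lower after a recurrence. For ALT/AST the rules are nested, so a site that follows Section 7.2.1.2 also satisfies Table 4.

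Much of this stands, and specific-over-general is the likelier reading. A reader might infer that the protocol directs restart at Grade 1 after hepatotoxicity, or leaves precedence wholly unsignalled; the documents support neither. But the closing paragraph is about re-evaluating held subjects and judges resolution by Table 4. Footnote c leads to a section that refers restarting back to Table 4. Investigator discretion permits departures without saying what the default is.

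A reader might also infer that QTcF prolongation without symptoms has no restart threshold. It has one, because the Table 4 row covers every Grade 3 or higher nonhematologic toxicity. The threshold would be lost only if Section 7.2.1.2 were made to govern without keeping it.

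Finally, Table 4 and Section 7.2.1.1 word the Grade 4 thrombocytopenia exclusion slightly differently. That is editorial and carries no weight here.

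**Conclusion.** The inconsistency is real and worth correcting, within limits. A site relying on Table 4 alone could restart after Grade 3 or higher ALT/AST elevation at least 7 days before Section 7.2.1.2 permits, or with Grade 1 diarrhea or rash still present. Near 42 days the texts can differ on restart versus permanent discontinuation. The exact day depends on an undefined hold count and on visit timing, so the cutoffs of day 35 or 36 are illustrative.

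The documents give no basis for estimating how many subjects this would touch. The wording is advisory, and Investigators may adjust it. A reader might infer that the trial's conclusions are at risk, but SAP 3.5 plans no inferential analysis, so the data effect is confined to some entries in descriptive tables. The reason to act is subject safety and uniform conduct.

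The TT conflict is minor. It affects visit timing and deviation records, and is softened by weekly re-evaluation during holds and by the 2-week carry-over of assessments.

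**What to change.** 1. State in Table 4 and in Section 7.2.1 that the event-specific restart criteria of Section 7.2.1.2 govern for every event named there: ALT/AST elevation, nausea/vomiting/diarrhea, rash, infections and cardiac events. Relabel the last Table 4 row as other Grade 3 or higher nonhematologic toxicity. Infections must be on the list; otherwise the relabelled row would send them to the general Table 4 criterion.
2. For QTcF prolongation without symptoms, keep the Table 4 threshold (Grade 1 or less, or baseline) explicitly. This is a clarification that step 1 makes necessary.
3. In Section 4.3, count the 7 days for the TT visit from the decision to terminate duvelisib, as Section 6.3 and Table 1 footnote b do.

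The cost is a short amendment or clarification letter. No visits, procedures or subjects are added.
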